Amended protocol for:

Observational Trial: Determining the accuracy of the HeartBeat Algorithm for calculating blood pressure

Contents

1. Introduction and Rationale	2
2. Study purpose	3
3. Study Design/Methodology	3
Trial registration.....	3
Protocol.....	3
Setting and clinicians	3
Recruitment plan	4
Interactions with participants and Data collection.....	5
Data Analysis.....	8
5. Confidentiality and security of data.....	9
6. Withdrawal from the study.....	10
List of Appendices	11
References	12

Observational Trial: Determining the accuracy of the HeartBeat Algorithm for calculating blood pressure

Funder: Centre for Aging and Brain Health Innovation (CABHI)

Investigator: [name]

Co-Investigator: [name]

Research Associate: [name]

Research Assistant: [name]

1. Introduction and Rationale

The gold standard instrument for blood pressure measurement is a mercury-filled sphygmomanometer with cuff and stethoscope (Canadian Agency for Drugs and Technologies in Health; Canadian Electronic Library, 2012). However, such a device is not the most convenient for client self-monitoring or virtual (remote) care. Thus, there is a desire for an accurate, reliable alternative for the traditional mercury-containing sphygmomanometer.

HeartBeat Technologies Ltd. (“Heartbeat”) has developed a novel approach to measuring blood pressure after an initial blood pressure reading using the conventional measurement method, supplemented by specific characteristics of a person (age, gender, height, weight, and heart rate), has established a “baseline measurement” for the person. The “novel approach” uses a finger pulse oximeter, the Contec CMS50EW device (Figure 1) (manufactured by Contec Medical Systems Co., Ltd., Shanghai, People’s Republic of China). The finger pulse oximeter detects the changes in blood volume directly below the person’s skin and indirectly measures oxygen saturation in the blood. The measurement is in the form of a photoplethysmogram (PPG) which is captured by the Contec oximeter and then, by Bluetooth technology, transmitted to a smartphone or tablet. A HeartBeat application, called MediBeat, on the smartphone or tablet then transmits the PPG to a server where a proprietary algorithm analyzes the baseline measurement for the person and the PPG to calculate the person’s current blood pressure.

Figure 1. Contec CMS50EW. Source:

http://www.contecmed.com/index.php?page=shop.product_details&flypage=flypage.tpl&product_id=118&category_id=27&option=com_virtuemart&Itemid=618

Heartbeat's intent is that the current blood pressure reading would then be made available to both the client and the health provider through separate web-based interfaces. Providers would be able to log onto the HeartBeat web-based application from anywhere to review and monitor the blood pressure of multiple clients, while clients can log onto the application to track their own measurements.

2. Study purpose

Though the Contec finger pulse oximeter has been approved for use by Health Canada (Licence No. 90629) and the FDA (<https://www.accessdata.fda.gov/scripts/cdrh/cfdocs/cfRL/rl.cfm?lid=465210&lpcd=DQA>), the proprietary algorithm developed by Heartbeat Technologies Ltd. has not been approved for use. The purpose of this study is to validate the accuracy of the algorithm as compared with the standard manual sphygmomanometer with stethoscope for measuring blood pressure. If the algorithm is shown to be accurate, Heartbeat Technologies Ltd. will apply to Health Canada and the FDA for approval for its use to measure blood pressure.

3. Study Design/Methodology

Trial registration

This study will be registered with ClinicalTrials.gov as it is one of two registered bodies approved and recommended by Health Canada. This will serve as a publicly accessible platform for patients and practitioners to understand the current study's objectives and goals, and be kept informed of the results.

Protocol

The European Society of Hypertension International Protocol revision 2010 for the validation of blood pressure measuring devices in adults (ESH-IP) (**Appendix A**) (O'Brien et al., 2010) will be followed precisely, except it will be modified to follow the extra guidance in the international consensus statement for validation (**Appendix B**) (Stergiou et al., 2018). The international consensus statement (Stergiou et al., 2018) reviewed the adequacy of the number of participants in a variety of established protocols including the ESH-IP, and recommended that, to increase study power and accuracy, the number of participants in a study following the ESH-IP should be at least 85 rather than 33 as in the 2010 version of the ESH-IP.

Setting and clinicians

Study site

The study site will be a room with a comfortable temperature and with no noise or other influences that may cause disturbance, such as telephones.

Health professionals involved

A supervisor and two observers are required to take the necessary recordings for this study. Three registered nurses will be identified for the study, with training and experience in blood pressure measurement. One will act as the supervisor and two will act as the observers, as specified in ESH-IP. These roles will be outlined below in the section entitled "Interactions with participants and data collection".

Clinicians who participate in this study will be trained and experienced in blood pressure measurement. They will be instructed to follow the ESH-IP guidelines for data collection and record all blood pressure measurements to the nearest 2 mmHg.

A familiarization session with the supervisor and the observers will be held in advance of interactions with participants. This session will involve a number of test measurements. The agenda for the session with the supervisor, who will be recording the data from the observers and from the novel approach, can be seen in **Appendix C**.

Conventional equipment

Two standard mercury sphygmomanometers, the components of which will be checked carefully before the study, will be used as the reference standards by the observers. They will be within 1m of where the observers will be when interacting with a participant, so that they will be able to follow the menisci at eye level from 40mmHg to 180 mmHg. Bladders of multiple sizes will be made available so that, on each subject, there is one of sufficient length to encircle 80%–100% of the arm circumference. The observers will be supplied with good quality non-electronic stethoscopes with well-fitting earpieces.

Heartbeat equipment

The pulse oximeter, the Heartbeat application (MediBeat), and the supervisor's smartphone (Samsung Galaxy Xcover 4 with Bluetooth connectivity) will be charged, and tested each day of interactions with participants. Prior to conducting the study session, the equipment will have to be calibrated for each participant. The first step of the calibration process is to manually enter the reference data (date of birth, height, weight, baseline manual blood pressure reading and heart rate). Once data is entered, and participant has been given 10 minutes of rest, the nurse supervisor will ensure the participant is seated comfortably, with their legs uncrossed, back supported, and their arm rested on the table at heart level. The nurse supervisor will then attach the Contec finger pulse oximeter to the participant's finger (opposite to the arm with the manual blood pressure cuff) and wait for a few seconds, to make sure a stable signal is received, and the device displays both the participant's pulse and SpO₂ values. Once the values are displayed, the nurse supervisor will hit the "Add session" button, and choose the correct device to connect to via Bluetooth. The calibration process will begin, indicated by the orange background, and the MediBeat application will display the participant's heartrate and SpO₂ values. It is critical that the participant does not move during the calibration process, which will last just over 1 minute. The background of the application will turn blue once calibration has completed successfully.

Recruitment plan

Inclusion/Exclusion Criteria

Healthy participants who are over the age of 25 and live or work in the North Simcoe Muskoka and Markham regions will be recruited to participate in this study. As outlined in the ESH-IP, only healthy subjects will be included this study; those who have heart arrhythmias, atrial fibrillations or atrial flutters, an inaudible Korotkoff sound, wounds of the upper arms/wrists, missing fingers, and/or an arm circumference of more than 55 cm will be excluded, in advance if at all possible, and at the study site if not previously excluded.

Recruitment will continue until the following quotas are met:

1. Numbers: At least 85 who fully complete the study protocol, and fall within the parameters listed in #3
2. Sex: At least 26 male and 26 female (each 30% of the total number of participants)
3. Blood pressure range: 26 to 31 subjects in each of the three SBP and three DBP recruitment ranges as shown in Form 3 – Study Results (**Appendix N**):
 - Low blood pressure (systolic: 0-129, diastolic: 0-79)
 - Medium blood pressure (systolic: 130-160, diastolic: 80-100)
 - High blood pressure (systolic: 161 or higher, diastolic: 101 or higher).

Participant Remuneration

To thank participants for their valuable time, they will be provided with a \$50 VISA pre-paid gift card at the end of the study visit.

Recruitment Methods

Recruitment flyers (**Appendix E**) will also be posted in public spaces at corporate offices and medical clinics, who have agreed to participate within Central Ontario, including Markham, Toronto, and North Simcoe Muskoka.

Recruitment emails (**Appendix F**) will be sent to all relevant employees located at corporate offices and medical clinics, who have agreed to participate within Central Ontario, including Markham, Toronto, and North Simcoe Muskoka, with a link to [contact] to indicate interest. Recruitment will be a two-step process.

Clinical staff, from clinics who have agreed to participate, will be provided with a short script (**Appendix G**) and Frequently Asked Questions (FAQ) document (**Appendix H**) to assist with the recruitment process. Individuals interested in participating can submit a consent to contact form (**Appendix I**) to the clinic staff, who will scan and send the forms to the research team. **Research assistant** will call individuals who had expressed their interest in participating to further explain the study (**Appendix J**) and ask if they would like to participate. The research assistant will then inform them about the consent form (**Appendix K**) that they will be asked to sign at the study site. The research assistant will provide the participant with information about a scheduled time for participating in the study and directions.

Interactions with participants and Data collection

Form 1 - Device information

Prior to the first interaction with a participant, the supervisor will fill in the information about the device in Form 1 of the ESH-IP (**Appendix D**). As noted above, the Contec CMS50EW device is an electronic finger pulse oximeter (Contec Medical Systems Co., Ltd, Qianhuangdao, China) that generates a PPG, which is then sent to HeartBeat's proprietary algorithm to calculate blood pressure.

Confirmation of appropriate setting conditions

[figure not shown]
Before involving any participant in the study, the **nurse supervisor** and **nurse observers 1 and 2** will ensure that the following requirements for the study site and equipment outlined by ESH-IP are met (O'Brien, 2010):

1. Environment
 - a. Comfortable temperature
 - b. No noises or disturbances (e.g. telephone, pagers) that could influence testing
 - c. Ambient noises are not at a level that could interfere with testing
2. Manual blood pressure device
 - a. Stethoscopes for using the sphygmomanometer have well-fitting earpieces.

Participant consent and interaction

At the study site, the following activities will be undertaken:

1. **Nurse supervisor** will provide the patient with the consent form and obtain the patient's consent (**Appendix L**) (signed consent forms – **Appendix K**) to be enrolled into the study. The nurse supervisor will photograph and email the consent forms to the research assistant once signed and witnessed.
2. **Nurse supervisor** will explain to the participant how their blood pressure measurements will be taken using the “conventional” and the “alternative” approaches.
3. **Nurse supervisor** will also complete the recruitment details in Form 2 in the “Recruitment details” section (**Appendix M**). **Nurse supervisor** will record the provided study participant's identification number onto the consent form.
4. The nurse supervisor will ask the participant to relax for 10–15 min.
5. **Nurse supervisor** will log onto the HeartBeat application to create a new patient profile and enter all baseline data (age, gender, height, weight, and heart rate).
6. After the period of relaxation, the nurse supervisor will make sure that the subject is seated with legs uncrossed and back supported, if the subject is not seated as described, the posture used must be recorded as a protocol adjustment.
7. **The nurse supervisor** will put the blood pressure cuff on the participant's left arm and ensure that the participant's arm is supported at heart level.
8. **The nurse supervisor** will put the Contec finger pulse oximeter on the participant's right index finger (and the participant will keep device on during duration of the study).
9. Blood pressure is measured as described in the following diagram:

10. Observer measurements will be recorded simultaneously by the observers on separate sheets. They will be checked immediately by the nurse supervisor and, if they differ by more than 4 mmHg, they will be taken again. Observers will be blinded from each other's measurements and from the device measurements.
11. Starting with the observers, the nurse supervisor will record the measurements sequentially by the supervisor, alternating between observers and the supervisors' reading of the device in the order BPA, BPB, BP1, BP2, BP3, BP4, BP5, BP6 and BP7 on Form 2.
12. **The nurse supervisor** will take a picture of the device measurements and those photographs will be emailed to the research assistant.
13. On a separate sheet, **the nurse supervisor** will keep a running total of the number of subjects recruited in the Low (LL and L), Medium (M), and High (H and HH), ranges for SBP (Box 219) and DBP (Box 220) on Form 2.
14. If any of the following occur during the study, **the nurse supervisor** will circle the appropriate item in Box 287 on Form 2 and exclude the subject:
 - Circle *Arrhythmias* if the subject is not in sinus rhythm throughout the study.
 - Circle *Device failure* if the device fails to record a measurement after three successive attempts.
 - Circle *Poor quality sounds* if the Korotkoff sounds are difficult to auscultate, regardless of the reason.
 - Circle *Observers disagreement* if the observers differ by more than 4 mmHg twice in the same subject.
 - Circle *Other* if the subject does not complete the study for any reason other than those listed and record the reason in Box 288.
15. In the event that an abnormal blood pressure reading is detected (e.g. if the blood pressure is outside clinically normal range for a specific client), one of the observers will

re-take the blood pressure to determine if the abnormal reading is accurate. If the abnormal blood pressure measurement is accurate, the **nurse supervisor** will take appropriate action as directed by professional standards. The abnormal blood pressure data will be recorded on Form 2.

Data Checking

During the data collection process, researchers will check the data daily to ensure the following as per the ESH-IP (O'Brien et al., 2010):

1. Ensure that the difference between the range with the highest count and lowest count does not exceed 19.
2. Ensure the overall systolic blood pressure is within the range of ≤ 100 to ≥ 170 mmHg and the overall diastolic blood pressure is within the range of ≤ 50 to ≥ 120 mmHg.
3. If the participants have a blood pressure outside the range of 90–180mmHg for systolic blood pressure and 40–130mmHg for diastolic blood pressure, only a maximum of 4 blood pressures readings outside of this range can be included in the analysis.
4. Ensure there are approximately 26-31 participants in each of the 3 blood pressure ranges (low blood pressure (systolic: 0-129, diastolic: 0-79), medium blood pressure (systolic: 130-160, diastolic: 80-100) and high blood pressure (systolic: 161 or higher, diastolic: 101 or higher)).

Data Analysis

[figure not shown]
The profile of the study participants will be described based on a demographic analysis conducted on data collected from the subject data form from the ESH-IP (**Appendix M**).

All collected data on Forms 1 and 2 will be sent to the researchers at the SE Research Centre, who will consolidate the data from the Forms 1 and 2 and analyze the data as specified in Form 3, the Study Results form from the ESH-IP (**Appendix N**) (O'Brien et al., 2010).

In order to pass the validation process, the device must pass both parts 1 and 2 based on the accuracy criteria table (**Appendix O**).

Plots

These are mean-difference plots, and the plots modelled from the data collected should be exactly as shown in the example plots below.

The x-axis of these plots represents blood pressures in the systolic range 80mmHg–190mmHg and the diastolic range 30 mmHg–140 mmHg. The y-axes represent errors from – 30mmHg to +30mmHg. Horizontal reference lines will be drawn at 5mmHg intervals from +15mmHg to – 15 mmHg. The mean of each device pressure and its corresponding observer pressure will be plotted against their difference with a point. Differences greater than 30mmHg will be plotted at 30 mmHg. Differences less than – 30mmHg will be plotted at – 30 mmHg. The same scales will be used for both SBP and DBP plots. Where points are superimposed, these will be indicated either by proportionately larger points or by different symbols.

5. Confidentiality and security of data

Electronic data

The data obtained from the pulse oximeter is captured by the Nurse supervisor's smartphone via Bluetooth connection. The smartphones and tablets used by SE Health nurses meet the requirements for all custodians of personal health information in Ontario. The HeartBeat application on the clinicians' smartphones or tablets encrypts the data for transmission to secure Google Servers within Canada, and the algorithm is also housed on those servers. The data outputs from the algorithm are then made available on a secure web-based password-protected portal to which only the researchers have access. The data will be downloaded by the researchers from the portal to password-protected computers which meet all the requirements for custodians of personal health information in Ontario.

Paper data

Paper data from the study will be photographed/scanned and emailed to the researchers at the SE Research Centre. Once received, the photographs, scans and emails will be deleted by the senders. The digital copies received in the SE Research Centre will be stored on a password protected computer that is accessible only by researchers from the SE Research Centre. All paper forms will be destroyed in keeping with SE Health's standards for destroying paper materials in accord with Ontario's *Personal Health Information Protection Act*.

Storage and data destruction

All electronic files will be kept secure on password protected computers and only research team members will have access to them. All paper-based data records will be photographed and stored electronically in password protected computers.

Written records (lists of participants and their email addresses if they wish to receive information from the study) will be secured in a locked file cabinet in the SE Research Centre, and then scanned to create digital copies of the written records will be stored on computers secured by passwords known only to the members of the research team for analysis. After scanning, the written records will be destroyed securely in accord with SE Health Care's procedure to comply with the standards of the *Personal Health Information Protection Act* of Ontario.

When analysis has been completed, the data will be transferred to secure servers owned by SE Health, which comply with the standards of the *Personal Health Information Protection Act*. Digital records will be destroyed securely within 72 months of the research project's end (i.e. in 2025) except those excerpts of the data used in final reports, publications, presentations and training materials. In the final reports, publications, presentation materials, and training materials that emerge from this research project, the data will be presented in such a way that the identity of the participant is not knowable by a reader or viewer.

6. Withdrawal from the study

Participants will be free to withdraw from the study at any time without penalty or affects to their care. Any data (e.g. blood pressure measurements) collected prior to the participant's withdrawal from the study but before its use in the study will be deleted and not used.

List of Appendices

- Appendix A – O’Brien (2010) European Society of Hypertension International Protocol (ESH-IP)
- Appendix B – Stergiou (2018) International Consensus Statement
- Appendix C – Training Agenda for Clinicians
- Appendix D – International Protocol Device & Study Details Form
- Appendix E – Recruitment Poster
- Appendix F – Recruitment Emails
- Appendix G – Brief information about the study
- Appendix H – Frequently Asked Questions (FAQ)
- Appendix I – Consent to contact for research
- Appendix J – Phone script for providing participant information
- Appendix K – Information and consent form for participants
- Appendix L – Script for obtaining participant consent
- Appendix M – International Protocol: Subject data form (amended)
- Appendix N – International Protocol Study Results Form
- Appendix O – International Protocol Accuracy Criteria Table

References

Heart and Stroke Foundation of Ontario and Registered Nurses' Association of Ontario (2005). *Nursing Management of Hypertension*. Toronto, Canada: Heart and Stroke Foundation of Ontario and Registered Nurses' Association of Ontario.

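### The algorithm is given each subject's own cuff pressure, and no visible analysis separates the finger signal's contribution from repeating that value; this limits what a pass may be said to show

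*Combined protocol and SAP*

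**What the plan says.** **Pressure as an input.** The Introduction says that "a proprietary algorithm analyzes the baseline measurement for the person and the PPG". The Heartbeat equipment section adds that "Prior to conducting the study session, the equipment will have to be calibrated for each participant", and the first step is to "manually enter the reference data (date of birth, height, weight, baseline manual blood pressure reading and heart rate".

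**When it is entered.** The same section continues "Once data is entered, and participant has been given 10 minutes of rest", which leaves open whether the reading is taken before or after the rest. Step 5 of Participant consent and interaction has the supervisor "create a new patient profile and enter all baseline data (age, gender, height, weight, and heart rate"; that list contains no pressure. No visible text says who takes the entered reading or whether it is BPA, and the visible Form 2 has no field for it.

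**Testing.** Steps 4 to 11 describe seated rest and then readings BPA, BPB and BP1 to BP7 in sequence. Payment is made "at the end of the study visit", which reads as a single visit. Form 2 limits the gap between adjacent readings to 30–60 seconds.

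**Grading.** Form 2 scores each device reading against the nearer of the previous and next observer means. Data Analysis refers to Form 3 and to the Appendix O limits, and Box 380 requires SBP and DBP both to pass. Form 3 uses BPA only for recruitment ranges and description.

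**Purpose.** Section 2 states the purpose as accuracy against the manual method, with regulatory applications to follow a favourable result. The intended use described before it is remote review, where "clients can log onto the application to track their own measurements".

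**The concern.** The reference method supplies both an input to the device and the standard it is judged by. If a subject's pressure during testing stays close to the entered value, returning that value with no use of the finger signal could meet Appendix O.

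A fail would still be informative. A pass would not by itself show that the algorithm follows a change in pressure, which is what readings taken later and away from the clinic rely on. The recruitment quotas do not help, because a repeated value carries each subject's own level into every range.

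**Working it through.** **1. The plan's own limits reproduce.** Form 3 Table 5 is scaled from 99 pairs to 255 and from 33 subjects to 85.

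- Two of: 73, 87, 96 × 255/99 = 188.03, 224.09, 247.27, giving 188, 224, 247.
- All of: 65, 81, 93 × 255/99 = 167.42, 208.64, 239.55, giving 167, 209, 240.
- Part 2: 24 × 85/33 = 61.82, giving 62; 3 × 85/33 = 7.73, giving 8.

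All eight match Appendix O.

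**2. Time span.** BPA to BP7 is nine readings and eight gaps: 8 × 30 s = 4 min to 8 × 60 s = 8 min, plus measuring time. The visible text plans no change in pressure and sets no limit on time or change since calibration.

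**3. Model of a repeater.** For subject *i*, let the true level be *m*, the shift since entry *s* (a mean, and a between-subject SD), and the within-session deviation *e* with SD σ and serial correlation 0 to 0.6.

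- Entered value: E = reading of (m + e₀).
- Observer means at BP1, BP3, BP5, BP7: Rⱼ = reading of (m + s + eⱼ), j = 1 to 4.
- All three device readings equal E.
- Scored difference: the smaller in absolute size of E − Rₖ and E − Rₖ₊₁, k = 1 to 3.

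The level *m* cancels, apart from rounding. From the documents come n = 85, recording to 2 mmHg, rounded-up observer means, the nearer-reading rule and the Appendix O limits. Assumed are σ, the shift, its between-subject SD, the correlations and an observer error SD of 1 mmHg. In the main cases E sits one step before BP1. Each setting used 1,500 to 6,000 trials.

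**4. Chance that a repeater passes, one component**

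| Assumed shift since entry | σ = 3 | σ = 4 | σ = 5 |
|---|---|---|---|
| None | 1.00 | 0.97–1.00 | about 0.7–0.9 |
| Mean 0, between-subject SD 3 | 0.84–0.86 | 0.55–0.63 | 0.24–0.33 |
| Uniform 3 mmHg fall | about 0.9 | about 0.6 | about 0.3 |
| 3 mmHg mean fall, between-subject SD 2 | 0.54–0.59 | 0.31–0.35 | 0.13–0.15 |
| 3 mmHg mean fall, between-subject SD 3 | 0.14–0.23 | 0.09–0.15 | 0.04–0.07 |
| None; E uncorrelated with session readings that correlate 0.6 | 0.97 | about 0.45 | 0.06 |
| As above, with a 3 mmHg fall | about 0.3 | 0.05 | 0.01 |

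With no shift, σ = 6 gives 0.24–0.53 and σ = 8 at most 0.02. A uniform 5 mmHg fall gives at most about 0.10 at any σ from 2 up. Rises of 3 to 5 mmHg gave the same figures as falls.

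**5. What makes a repeater fail.** At σ = 5 with no shift or serial correlation, an average of 197.3 pairs lie within 5 mmHg (limit 188) and Part 1 is passed in effectively every trial. The average number of subjects with none of three within 5 mmHg is 7.40 against a cap of 8, and Part 2 is passed in 0.68 of trials. That cap is the main protection.

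**6. Effect of the nearer-reading rule.** At σ = 4 with no shift or serial correlation, a repeater passes 0.97 of the time under the rule and about 0.37 if only the previous observer reading counts.

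**7. Both components.** A joint pass cannot be likelier than the lower single rate. With independence assumed, no shift and SDs of 5 (SBP) and 4 (DBP), it is 0.67–0.90.

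**8. Would it be visible?** An exact repeater would show identical values in Boxes 255, 257 and 259. Random jitter of SD 1–3 mmHg would hide this and still pass at 0.99–1.00 for σ = 4 with no shift.

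**The case against.** The plan does not claim that a pass proves tracking. Its purpose is agreement with the manual method, Appendix O tests that, and the phrase about clients tracking measurements may mean no more than viewing them in an application. This stands: the pass rule is not defective. The Introduction does, however, speak of calculating the person's current pressure, so a limit on interpretation is reasonable.

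The high pass rates also depend on a favourable sequence. If the reading is entered before the rest, and calibration, BPA and BPB then come before BP1, the lower rows of the table may be the relevant ones. This stands too, because the documents do not settle the timing.

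A reader might infer that a repeater passes whenever the within-session SD is about 5 mmHg or less and the shift is under about 4 mmHg. The table does not support that: inside that region the rate falls as low as 0.01 once the shift varies between subjects or the entered reading is less close to the session. A reader might also infer that Form 3 routinely removes subjects whose pressure moved. Under Table 3 that replacement applies only when a distribution limit fails, and only to the minimum number needed.

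Finally, the step 9 diagram, the figure under Data Analysis and Appendices A, B and D are not shown, and the plan says the ESH-IP "will be followed precisely, except it will be modified to follow the extra guidance in the international consensus statement for validation". Any statement about missing analyses is therefore limited to the visible text.

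**Conclusion.** The point holds as a limit on interpretation and is one for the sponsor to consider. The subject's manual pressure is an input, grading is against the nearer manual reading, and no visible analysis compares the device with the entered value alone.

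A repeater is likely to pass a component only if four conditions hold together: within-session SD of about 4–5 mmHg or less; a small mean shift since entry; little variation in that shift between subjects; and, at SD 4–5, an entered reading about as close to the session readings as they are to each other. All SDs, shifts and correlations are assumed, because the documents give none.

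Two stronger conclusions are tempting and unsupported. One is that the algorithm merely returns the entered pressure; nothing in the documents shows this. The other is that Appendix O is invalid here; it remains a sound test of agreement at rest after calibration.

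**What to change.** 1. Reconcile the Heartbeat equipment section with steps 4–7 of Participant consent and interaction on whether and when a manual pressure is entered. Record on Form 2 the SBP and DBP entered, the time they were taken, and whether they are BPA.
2. Leave the Appendix O pass rule unchanged. Pre-specify, as supporting description, the Appendix O counts obtained by repeating the entered value beside the device's counts, for SBP and DBP, with the mean and SD of observer minus entered value. If repetition fails where the device passes, this strengthens the sponsor's case.
3. Word a pass as agreement at rest after calibration in the same visit.
4. Optional: a descriptive regression of (device minus entered) on (observer minus entered), with the entered value as covariate and subject-clustered intervals.
   - For the observer, use the average of the previous and next observer means (Boxes 239–246). Boxes 281–286 are chosen for closeness to the device: with them a jittered repeater gave slopes of 0.04–0.50, against 0.00 with the averages.
   - Use BPA as baseline only if BPA was the value entered.
   - State that the slope is attenuated. A device that tracks fully gave 0.63–0.98 in simulation, so a slope below 1 does not by itself show partial tracking, and a wide interval is inconclusive.
   - Do not make the slope a condition for passing.

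Cost: a few Form 2 fields, a short paragraph in Data Analysis and little extra analysis, with no added subjects or procedures. The downside is a possibly narrower claim.
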